#### **6. TRIAL PARTICIPANT DISPOSITION**

Enrollment will take place at two sites: Birmingham and Pittsburgh, USA.

##### **6.1 Disposition of Participants**

###### **6.1.1 Screening and Enrollment**

Dates of site activation, first enrollment, and last enrollment, as well as the number of participants screened, number and percentage of participants enrolled, and the screening-to-enrollment ratio will be displayed in a table overall and by site.

###### **6.1.2 Retention**

A table will display for each visit the number and percentage of participants who are expected, retained, missing, and lost-to-follow-up or terminated with respect to that visit, overall and by site.

###### **6.1.3 Treatment Discontinuation**

The number and percentage of participants who ended product use early, as well as the reasons for terminating product use early, will be presented in a table overall and by site.

###### **6.1.4 Study Discontinuation**

The number and percentage of participants who completed the study, as well as the reasons for non-completion, will be displayed in a table overall and by site.

### 6.1.5 Completion of Procedures

The completion of required and expected procedures will be displayed in a table overall and by site. The table will display the number and percentages of participant-visits for each procedure.

### 6.2 Treatment Exposure

The number and percentage of enrolled participants administered the one insert dosing regimen at Visit 3 and then number of participants administered the two inserts dosing regimen at visit 7 will be displayed overall and by site. Participants will be classified into groups by dosing regimen based on the time from dosing up until just before the next higher dosing regimen is administered (e.g., for the one insert dosing regimen, any safety endpoints which occur between the time of one insert administration at Visit 3 up until, but not including, the time of the two insert administration at Visit 7.)

If applicable, the number and percentage of participants who had study product held during follow-up will be displayed overall and by site (along with the reasons why product was held).

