## 7.4 Follow-up Visits

### 7.4.1 Dosing – Visits 3 and 7

The first dosing visit (Visit 3) should occur at least 7 days after the Enrollment Visit. The second and final dosing visit (Visit 7) should occur at least 7 days after the last tissue sampling visit following Dose 1 (following Visit 5 or 6 with a 1- to 7-week washout period).

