**Table 13: 24-hour Post-Dosing Visits**

24-Hour Post-Dosing Visits - Visits 4 and 8		
Component	Procedures	
Administrative and Regulatory	
 
Review/update locator information
 
Provide reimbursement
 
Schedule next visit/contact
 
	
Behavioral/Counseling	
 
HIV pre- and post-test counseling*
 
HIV/STI risk reduction counseling*
 
Protocol counseling
 
Behavioral assessment (Brief CASI)
 
	
Clinical	
 
Review/update medical history
 
Review/update concomitant medications
 
Perform targeted physical examination*
 
Perform genital examination*
 
Perform pelvic examination* ▲
 
Perform rectal examination
 
Treat or prescribe treatment for RTI/UTI, or STIs*
 
Provide available test results
 
Collect/update AEs
 
	
Laboratory	Pharyngeal	
 
NAAT for GC/CT*
 

	Urine	
 
NAAT for GC/CT* ▼
 
Urine dipstick/culture*
 
Pregnancy test* ■
 

	Blood	
 
CBC with differential and platelets*
 
Chemistries (AST/ALT/creatinine)*
 
Syphilis serology*
 
HIV-1/2 test*
 
Blood for PK
 

	Pelvic▲	
 
CVF for PK ☼
 
CVF for PD ☼
 
CVF for microflora ☼
 
NAAT for GC/CT/TV*
 

	Anorectal	
 
Rectal fluid for PK ☼
 
Rectal fluid for PD ☼
 
Rectal fluid for microbiome ☼
 
Rectal tissue for PK ☼
 
Rectal tissue for PD ☼
 
Rectal tissue for biomarkers ☼
 
NAAT for GC/CT*
 

Study Product/Supplies		
 
Offer condoms
 

\* If indicated ▲ Participants assigned female sex at birth and if anatomy allows ▼ If pelvic GC/CT cannot be performed ■ Participants of childbearing potential ☼ Group 2 only

### 7.4.3 Other Post-Dosing Visits – Visits 5, 6, 9, and 10

The 48-hour Post-Dosing Visits (Visits 5 and 9) should occur between 44 and 52 hours (+/- 4 hours) after each dosing visit. The 72-hour Post-Dosing Visits (Visits 6 and 10) should occur between 66 and 78 hours (+/- 6 hours) after each dosing visit.

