#### 7.4.4 Final Contact/Early Termination Visit

The *Final Contact* (Visit 11) should occur approximately 3-7 days following Visit 10 and may be conducted over the phone. This contact will also serve as the participant's study termination. Participants who permanently discontinue study product and follow-up visits prior to study completion will be asked to complete an Early Termination Visit, if willing.

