### **8.3 Adverse Events Definitions and Reporting Requirements**

#### **8.3.1 Adverse Events**

An AE is defined as any untoward medical occurrence in a clinical research participant administered an investigational product and which does not necessarily have a causal relationship with the investigational product. As such, an AE can be an unfavorable or unintended sign (including an abnormal laboratory finding, for example), symptom or disease temporally associated with the use of an investigational product, whether or not considered related to the product. This definition is applied to all study groups, and is applied to all groups beginning at the time of enrollment (i.e., once a participant is randomized) through the termination visit. The term “investigational product” for this study refers to the TAF/EVG Insert, 20/16 mg.

Study participants will be provided instructions for contacting the study site to report any untoward medical occurrences they may experience. In cases of potentially life-threatening events, participants will be instructed to seek immediate emergency care. Where feasible and medically appropriate, participants will be encouraged to seek evaluation where a study clinician is based, and to request that the clinician be contacted upon their arrival. With appropriate permission of the participant, whenever possible, records from all non-study medical providers related to untoward medical occurrences will be obtained and required data elements will be captured in the study database. All participants reporting an untoward medical occurrence will be followed clinically until the occurrence resolves (returns to baseline) or stabilizes.

Study site staff will document in source documents and in the study database all AEs reported by or observed in enrolled study participants regardless of severity and presumed relationship to study product. AE severity will be graded per the DAIDS Table for Grading Adult and Pediatric Adverse Events, Corrected Version 2.1, July 2017 and/or Addenda 1, 2 and 3 (Female Genital [Dated November 2007], Male Genital [Dated November 2007] and Rectal [Clarification Dated May 2012] Grading Tables for Use in Microbicide Studies).

Please note:

- Asymptomatic BV and asymptomatic candidiasis will not be reportable AEs;  
*Note:* Asymptomatic BV and asymptomatic candidiasis will be captured on the CRF that captures STI results.

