**Figure 1: MTN-039 Study Visit Schedule**

As displayed in Figure 1, participants will receive a rectally administered dose of one TAF/EVG insert at Visit 3 and have safety laboratory tests, PK and PD assessments performed over the next three days (Visits 4, 5, and 6). Participants will self-administer a saline enema at home the evening prior to a clinic dosing visit (Visits 3 and 7). After a washout period of one to seven weeks following the last tissue sampling associated with one TAF/EVG insert dosing, participants will receive dosing of two TAF/EVG inserts at Visit 7 and have safety laboratory tests, PK and PD assessments performed over the next three days (Visits 8, 9, and 10). A final study contact will occur approximately 3-7 days after Visit 10 and may be conducted over the phone.

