### 8.1 Primary Safety Analyses

The primary safety endpoint is defined as follows:

All Grade 2 and higher AEs

The number and the percentage of participants experiencing each safety endpoint will be tabulated by dosing regimen (one insert or two inserts). This table will display a summary for any primary safety endpoint and for each individual safety endpoint. Each participant will contribute once in each category

(i.e., only for highest severity AE for each participant) for the calculation of event rates for each dosing regimen. Exact binomial confidence intervals (Clopper-Pearson) will be calculated for each safety endpoint, even if no events occur for an endpoint for a particular dosing regimen.

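### The by-dose safety table counts adverse events over about 9-52 days for one insert but about 6-10 days for two, so its two percentages are risks over different durations

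*SAP*

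**What the plan says.** **Which events belong to which dose.** SAP 6.2 classifies participants "based on the time from dosing up until just before the next higher dosing regimen is administered". For one insert it spells this out as "any safety endpoints which occur between the time of one insert administration at Visit 3 up until, but not including, the time of the two"-insert administration at Visit 7. No higher regimen follows two inserts, so that window ends when AE collection ends. Protocol 8.3.1 says the AE definition is "applied to all groups beginning at the time of enrollment (i.e., once a participant is randomized) through the termination visit".

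**When Visit 7 falls.** Protocol 7.4.1 places it "following Visit 5 or 6 with a 1- to 7-week washout period". The SAP's text under Figure 1 agrees: "After a washout period of one to seven weeks following the last tissue sampling associated with one TAF/EVG insert dosing". The last tissue sample is at 48 hours in Group 1 and 72 hours in Group 2.

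**When follow-up ends after two inserts.** Protocol 7.4.4 says the final contact "should occur approximately 3-7 days following Visit 10 and may be conducted over the phone", and Visit 10 is the 72-hour visit.

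**What is tabulated.** The primary endpoint is all AEs of Grade 2 or higher, whatever the cause. SAP 8.1: "The number and the percentage of participants experiencing each safety endpoint will be tabulated by dosing regimen (one insert or two inserts"), with a Clopper-Pearson interval for each. Neither document specifies person-time, an equal risk window or a cut-off after dosing for this table. Protocol 10.7.2 allows the doses to be compared descriptively for tolerability and rules out formal comparison.

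**The concern.** A crude percentage of participants with an event grows with the time over which events are counted. The endpoint includes events unrelated to the product, and the one-insert window contains the whole washout while the two-insert window stops soon after the last sample. With a long washout, incidental events would collect under one insert and the higher dose would look relatively safer than it is. In a study with no formal dose comparison, readers rely on this table, so its two columns should measure the same thing.

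A related gap is that AEs are collected from Enrollment, at least 7 days before the first dose, but the SAP 8.2 tables are by dosing regimen and SAP 6.2 defines no pre-dose category. Events after the Enrollment biopsies and before any product therefore have no table.

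**Working it through.** **The plan's own figure.** Protocol Table 18 gives an upper bound of 16.8% for 0/20. Clopper-Pearson: 1 - 0.025^(1/20) = 16.8%. The other upper bounds (24.9, 31.7 and 37.9%) also reproduce. The interval method is sound; the question is what the percentage refers to.

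**Window lengths from the visit intervals**

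| Window | Shortest | Longest |
|---|---|---|
| One insert, Group 1 (Visit 5 at 2 d + washout 7-49 d) | 2 + 7 = 9 d | 2 + 49 = 51 d |
| One insert, Group 2 (Visit 6 at 3 d + washout 7-49 d) | 3 + 7 = 10 d | 3 + 49 = 52 d |
| Two inserts (Visit 10 at 3 d + final contact 3-7 d) | 3 + 3 = 6 d | 3 + 7 = 10 d |

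Visit tolerances barely change this. With the 44- to 52-hour and 66- to 78-hour visit windows, one insert spans 8.8 to 52.3 days and two inserts 5.8 to 10.3 days. The mid-range ratio is 30.5/8 = 3.8. The extremes are 9/10 = 0.9 and 52/6 = 8.7.

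**Effect on the percentages.** The documents give no background rate of Grade 2 or higher AEs and no expected washout distribution. I assume a constant drug-unrelated hazard h of 0.5% per day (range 0.2-1%) and no drug effect. Expected percentage = 1 - exp(-h × days); for example, 1 - exp(-0.005 × 30) = 13.9%.

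| Days, one v two inserts | Expected % at 0.5%/day | At 0.2%/day | At 1%/day | Expected participants of 20 at 0.5%/day |
|---|---|---|---|---|
| 9 v 10 | 4.4 v 4.9 | 1.8 v 2.0 | 8.6 v 9.5 | 0.88 v 0.98 |
| 9 v 8 | 4.4 v 3.9 | 1.8 v 1.6 | 8.6 v 7.7 | 0.88 v 0.78 |
| 30 v 8 | 13.9 v 3.9 | 5.8 v 1.6 | 25.9 v 7.7 | 2.8 v 0.8 |
| 52 v 8 | 22.9 v 3.9 | 9.9 v 1.6 | 40.5 v 7.7 | 4.6 v 0.8 |

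**Chance that one insert shows the higher count with no drug effect** (two independent binomials, n = 20 each, h = 0.5% per day): about 0.36 at 9 v 8 days, 0.80 at 30 v 8 and 0.95 at 52 v 8. At 30 v 8 days it is 0.59 for 0.2% per day and 0.92 for 1% per day.

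Rounded to whole participants, the 30 v 8 case is 3/20 against 1/20. By Table 18 a reader would see 15% (3.2-37.9) against 5% (0.1-24.9), produced by window length alone.

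**With equal windows.** At 6 days after each dose, the expected background is 1 - exp(-0.005 × 6) = 3.0% in both columns.

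**Pre-dose interval.** By Protocol Table 16, Enrollment has 7 + 4 = 11 biopsies in one sigmoidoscopy. Each dosing period has 7 + 4 + 11 = 22 and then 4 + 11 = 15 biopsies, 37 in two sigmoidoscopies.

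**The case against.** **A reader might infer that the table is biased towards two inserts.** The documents do not support that as a net statement. Protocol Table 14 and Appendix I require blood count, chemistries and HIV testing after dosing only at Visit 10; elsewhere they are done if indicated. (The SAP's text under Figure 1 mentions safety laboratory tests after both doses, but the protocol schedule does not require them after the first.) Laboratory events are therefore more likely to be found under two inserts. The size of the window effect also depends on the washouts actually used; near 7 days it is negligible or reverses. Both limits stand.

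**No test or dose-selection rule uses the table.** Each interval describes one dose, and counting until the next dose keeps late one-insert events visible in a first rectal study. This stands as a reason to keep the full-window table. It does not make the columns comparable, and the protocol allows a descriptive comparison.

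**Other tables help.** SAP 8.2 plans AEs by relationship and by severity for each regimen, plus a cumulative listing. Protocol 8.3.1 excludes expected procedural bleeding, urgency, bloating and flatulence from reportable AEs. So it would be too strong to say that incidental or procedural events cannot be separated at all. But relatedness is judged open-label, and the primary table does not use it.

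**A reader might treat the pre-dose interval as an internal control.** It is not a matched one: 11 biopsies in one sigmoidoscopy against 37 in two. An excess after dosing could still be procedural.

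**One feature works the other way.** Protocol 9.4 requires a hold and consultation after a related Grade 2 or any Grade 3 AE, and SAP 3.2 drops undosed participants from that dose's analyses. This could remove susceptible participants from the two-insert column. It is not quantified here.

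**Conclusion.** The concern holds as a problem of definition. Under SAP 6.2 and 8.1 the two columns are risks over about 9-52 and 6-10 days. When washout is well above the minimum, background events alone make two inserts look relatively safer; near the minimum they do not. The event figures rest on an assumed constant hazard and on independence between periods; the day ranges rest only on the documents' visit intervals and on AE collection ending at the final contact. Net bias in either direction is not shown, because the laboratory schedule pulls against the window effect. With no formal comparison planned and partial help from SAP 8.2, this is a should-fix.

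**What to change.** In SAP 6.2 and 8.1:

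- State when the two-insert window ends. Keep the full-window table, and show person-days and Grade 2 or higher events per person-week for each dose.
- Add the by-dose percentage with its exact interval over an equal post-dose window, and use that display whenever the doses are compared descriptively. About 5 to 6 days is suitable. The earliest final contact is nominally 6 days after dosing, but about 5.75 days if Visit 10 is at 66 hours (66/24 + 3), so 5 days is safer. The earliest Visit 7 is about 8.8 days after the first dose (44/24 + 7), so the window fits there too.
- List later one-insert events separately so that none is lost.
- Footnote that routine laboratory tests are required after dosing only at Visit 10; an equal window does not make laboratory detection equal.
- Tabulate AEs between Enrollment and Visit 3 in a pre-dose column, labelled a rough reference, with the biopsy and sigmoidoscopy counts stated.

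The person-week rate should not replace the equal window: reactions clustered soon after dosing would be diluted by a long washout.

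The cost is SAP wording and a few table columns from data already collected. The common-window display will count fewer events, so its intervals will say less about late effects; the retained full-window table covers those.

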### 6.3 Protocol Deviations

Protocol deviations occurring in MTN-039 will be summarized in a table of each type of deviation by site and overall, and in a listing of deviation events.

These data will be reviewed prior to the analysis of the primary and secondary endpoints to determine if any protocol deviations in this study impact participant eligibility or treatment administration and subsequently necessitate adjustments to the analysis set.

## 7. BASELINE DATA

Baseline participant demographic characteristics such as age, sex at birth, ethnicity, race, gender, sexual orientation, height, weight, and body mass index (BMI) will be summarized and displayed in tables overall and by site, and in tables overall and by sex at birth. Descriptive statistics will be presented for age, height, weight, and BMI. Frequency counts and percentages will be presented for sex at birth, ethnicity, race, gender, and sexual orientation. No formal comparisons are planned.

Individual participant baseline characteristics (medical history and results from baseline anorectal exam findings, pelvic exam findings, physical exam findings, STI test findings, hematology, and local laboratory results) will be presented in listings.

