**2.3 Randomization**

There will be no randomization to dose of TAF and EVG (one or two inserts) in this open-label, single arm, and two-period trial.

At study randomization upon enrollment, participants will be assigned to one of two sampling group schedules for collection of rectal tissue (collected with flexible sigmoidoscopy), rectal fluid, and cervicovaginal fluid (if applicable):

Group 1: Visits 3, 5, 7, and 9

Group 2: Visits 4, 6, 8, and 10

Notes: Both sampling groups 1 and 2 will provide blood at Visits 3-10. At Visits 3 and 7, both sampling groups will provide rectal fluid and cervicovaginal fluid (if applicable) – Group 1 at 2- and 6-hours post-dose, and Group 2 at 4-hours post-dose. At Visits 3 and 7, rectal tissue sampling will be conducted in Group 1 participants at 2-hours post-dose. All sampling times are approximate; allowable windows and detailed instructions are provided in the MTN-039 SSP Manual.

Each participant will have a total of 5 flexible sigmoidoscopies for rectal tissue sampling:

- at baseline (both sampling groups, 1 set of biopsies)
- at 2- and 48-hours post-dose for each dose (Group 1 only, 4 sets of biopsies)
- at 24- and 72-hours post-dose for each dose (Group 2 only, 4 sets of biopsies).

Randomization will be stratified by sex at birth to incorporate at least three participants assigned female sex at birth in each sampling group.

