## **2.5 Sample Size and Power**

The study is designed for a total accrual of twenty (20) participants, which gives sufficient power for the detection of adverse events as described in the protocol. Descriptive safety analyses and pharmacokinetic analyses are planned with no formal statistical testing.

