### *Blood Concentrations*

For blood, EVG, TAF, and TFV concentrations can be plotted over time for each individual participant, and PK parameters (defined below) may be calculated for each participant and then summarized across all participants.

Displays of blood concentration data include:

- Tables summarizing the distribution of concentrations at each sampling time point for each dose administration (3 tables, one for each drug, with a column for each dose administration).
- Plots of individual participant concentration-time data presented in a panel for each dose administration (6 panels of plots (1 panel for each dose administration and drug)).
- Individual participant concentration-time data will also be overlaid on a single plot for each dose administration and drug (6 plots).
- Plots of mean/median concentration at each time point (with 95% C.I.) for each dose administration and drug (3 panels, one for each drug, with 2 plots (1 for each dose administration)).
- Listings of individual participant PK parameters for each dose administration and drug (6 listings).
- Tables summarizing the distributions of PK parameters across all participants for each dose administration and drug (6 tables).

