### *Rectal Fluid and Rectal Tissue Concentrations*

For rectal fluid and rectal tissue, the concentration-time profile will consist of data from different participants at different sampling time points. Individual participant PK parameters will not be calculated for concentration data from rectal fluid and rectal tissue since data were not collected at each time point for each participant.

Displays of rectal fluid and rectal tissue concentration data include:

- For each matrix (RF, RT), tables summarizing the distribution of concentrations at each sampling time point for each dose administration and drug (7 tables (3 for RF, 4 for RT) with a column for each dose administration).
- For each matrix (RF, RT), scatter plots of drug concentration-time data for each dose administration (7 panels (3 for RF, 4 for RT) with 2 plots (1 for each dose administration)).
- For each matrix (RF, RT), plots of mean/median concentration at each time point (with IQR or 95% C.I., as appropriate) for each dose administration (7 panels (3 for RF, 4 for RT) with 2 plots (1 for each dose administration)).

The PK parameters are:

$C_{max}$	Maximum observed drug concentration.
$C_{last}$	Last observed drug concentration.
$t_{max}$	Time of occurrence for $C_{max}$
$AUC_{0-t}$	Area under the drug concentration-time curve to the time of the last measurable concentration.
$AUC_{0-\infty}$	Area under the drug concentration-time curve to infinite time. Equal to $AUC_{0-t}$ plus $AUC_{t-\infty}$ = $(C_{last} / k_e)$ .
$k_e$	Terminal elimination rate constant.

---

$t_{1/2}$	Half-life of drug elimination in the terminal phase.
%AUC ex	Percentage of AUC 0-∞ obtained by extrapolation, calculated as $[(C_{last} / k_e) / AUC_{0-∞} * 100]$

The time, in hours, to each sample collection time is calculated from the time of dose administration. The area under the curve (AUC) is calculated for each participant using the trapezoidal method from the time of dose administration to the time of the last sample collection (AUC0-t), typically at 72h.

Concentrations after  $C_{max}$  are used to determine the terminal elimination rate constant ( $k_e$ ) and associated half-life of drug elimination in the terminal phase ( $t_{1/2}$ ), when at least three such concentration values are available, according to the following formulas:

$$k_e = \ln(C_1/C_2) / (t_2 - t_1)$$

$$t_{1/2} = \ln(2) / k_e$$

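### Rectal fluid and tissue time points alternate between the two sampling groups, but the SAP plans no rectal display by group and no within-person contrast

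*SAP*

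**What the plan says.** Dose order is fixed. The only randomised factor is the sampling schedule: "participants will be assigned to one of two sampling group schedules for collection of rectal tissue", as well as rectal and cervicovaginal fluid (SAP 2.3). On the allocation, the SAP says: "Randomization will be stratified by sex at birth to incorporate at least three participants assigned female sex at birth in each sampling group". It states no allocation ratio and no stratification by site.

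On dosing days rectal fluid is taken from "Group 1 at 2- and 6-hours post-dose, and Group 2 at 4-hours post-dose" (SAP 2.3). SAP Section 9, Table 1 gives the full pattern:

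| Matrix | 2 h | 4 h | 6 h | 24 h | 48 h | 72 h |
|---|---|---|---|---|---|---|
| Rectal fluid | G1 | G2 | G1 | G2 | G1 | G2 |
| Rectal tissue | G1 | – | – | G2 | G1 | G2 |

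For these matrices SAP 9.2 states that "the concentration-time profile will consist of data from different participants at different sampling time points", and for that reason it drops individual rectal PK parameters. It plans summary tables by time point with a column per dose, scatter plots, and plots of the mean or median at each time point. None is split by group.

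The other outputs do not use sampling group either. Baseline characteristics "will be summarized and displayed in tables overall and by site, and in tables overall and by sex at birth" (SAP Section 7). Blood is drawn from both groups at every time, but its PK parameters "may be calculated for each participant and then summarized across all participants" (SAP 9.2). Summaries of collection times are overall and by site (SAP Section 9).

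**The concern.** Rectal pharmacokinetics is a primary objective, and Protocol 10.7.2 intends the time points to describe the course from soon after dosing, through the peak, into early elimination. A reader will look for that course by comparing neighbouring time points. In this design every such comparison is between two different sets of people.

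If one group happens to contain people with higher rectal exposure, the difference enters each step of the profile with alternating sign. A flat course in fluid at 2, 4 and 6 h could look like a peak at 4 h, or a real peak could be flattened. In tissue, the apparent fall from 2 h to 24 h could be exaggerated or hidden. The design does hold within-person information at each dose, from three fluid times and two tissue times per participant, but no planned table or figure uses it.

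**Working it through.** **The plan's own figures.** The documents give no design figure for this point. Their only design figures concern safety, and these reproduce. P(at least one event | n = 20, rate 5%) = 1 − 0.95^20 = 64.2%. The exact upper 95% bound for 0/20 is 1 − 0.025^(1/20) = 16.8%.

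**How many steps cross groups.** From SAP Table 1, all 5 steps between adjacent fluid times and all 3 between adjacent tissue times go from one group to the other. Contrasts that stay within a group are 2, 6 and 48 h (G1) and 4, 24 and 72 h (G2) in fluid, and 2 to 48 h (G1) and 24 to 72 h (G2) in tissue.

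**Inputs for the size of a chance difference.**
- N = 20: "The study is designed for a total accrual of twenty (20) participants" (SAP 2.5). A split of 10:10 is assumed, because no ratio is stated.
- Between-participant CV: none is given for rectal samples. Protocol 2.7.2 gives 25.5% for EVG AUC and 55.8% for TAF AUC, both in plasma after oral dosing in adolescents. They serve only as illustrations. CVs of 100% and 150% are assumptions added to show a range.

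**Formulas** (log-normal concentrations, identical true levels in the two groups):
- SD on the log scale: s = √ln(1 + CV²)
- SE of the difference in log means: s × √(1/10 + 1/10) = 0.447 s
- 95% chance range of the ratio of geometric means: exp(±1.96 × SE)

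For CV 55.8%: s = √ln(1.311) = 0.521; SE = 0.447 × 0.521 = 0.233; exp(1.96 × 0.233) = 1.58.

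| CV | s | 95% chance range | P(differ by >1.25-fold) | P(differ by >1.5-fold) |
|---|---|---|---|---|
| 25.5% (oral EVG plasma) | 0.251 | 0.80–1.25 | 5% | under 0.1% |
| 55.8% (oral TAF plasma) | 0.521 | 0.63–1.58 | 34% | 8% |
| 100% (assumed) | 0.833 | 0.48–2.07 | 55% | 28% |
| 150% (assumed) | 1.086 | 0.39–2.59 | 65% | 40% |

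Splits of 9:11 or 8:12 move the factor 0.447 only to 0.449 or 0.456.

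**Effect on the profile.** Suppose true fluid levels are equal at 2, 4 and 6 h and Group 2 runs 1.58-fold higher. The summaries then read 1.00, 1.58, 1.00, an apparent peak at 4 h. If instead the true 4 h level is 1.58-fold higher and Group 2 runs at 0.63, the 4 h summary is 1.58 × 0.63 = 1.00 and the peak disappears.

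**What a within-person contrast gains.** Let ρ be the correlation between two log concentrations in the same person. The variance of the mean log difference is 2s²/10 between two groups of 10, but 2s²(1 − ρ)/10 within 10 people. The within-person contrast is more precise for any ρ above zero. The documents give no ρ, so the gain cannot be quantified.

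**The case against.** The strongest reply is that this is ordinary sampling error in a descriptive study: "Descriptive safety analyses and pharmacokinetic analyses are planned with no formal statistical testing" (SAP 2.5). Allocation is random and stratified by sex at birth. Each rectal summary already comes from one group only, and SAP 9.2 openly says that the profile mixes participants. It specifies no line joining the points. It provides for 95% confidence intervals (or the IQR in the rectal figures), and intervals convey part of this noise. All of that stands. What the intervals do not show is which points share the same people.

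A reader might infer that the rectal time course is biased, that one curve will be drawn through both groups, or that nothing in the outputs would reveal a group difference. The documents support none of these. A difference would arise by chance. The joined curve is not specified. Individual concentration listings (SAP 9.1) and individual blood plots and parameter listings (SAP 9.2) would let a reader rebuild the groups from who was sampled when. The accurate statement is narrower: no planned display does this.

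A reader might also infer that comparing blood PK between groups would settle whether the groups are comparable. It would not. The product acts locally, the macaque vaginal insert study found no measurable systemic exposure (Protocol 2.6.2.1), and low plasma levels are expected with the vaginal insert in women (Protocol 2.7.2). Similar blood levels would not prove similar rectal exposure.

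Finally, the larger fold-differences rest on assumed CVs. At the documents' own CVs the range is modest.

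**Conclusion.** The point holds as a minor improvement to the presentation of a primary objective. All 8 adjacent rectal steps (5 fluid, 3 tissue) compare different people, and no planned output separates the groups or uses the within-person data.

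With 10 per group, chance alone could produce a group ratio up to 1.25-fold (CV 25.5%) or 1.58-fold (CV 55.8%), and up to 2.1- or 2.6-fold if rectal CVs are 100% or 150%. These figures assume 1:1 allocation and log-normal data, and take the CV as the whole spread between participants at one time. Only the part of that spread that is stable within a person is removed by within-person contrasts.

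Two things limit the consequence. Participants keep their group for both doses, so a stable proportional group effect cancels in the one- versus two-insert comparison at a given time. Trends within a group are also unaffected. The planned tables are not wrong; they leave unused a protection that the design already provides.

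**What to change.** In SAP 9.2, under rectal fluid and rectal tissue:

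1. Mark Group 1 and Group 2 separately in the scatter and mean/median figures, and join only points from the same group.
2. Tabulate within-person ratios by dose and drug: fluid 6 h/2 h and 48 h/2 h (Group 1), 24 h/4 h and 72 h/4 h (Group 2); tissue 48 h/2 h (Group 1) and 72 h/24 h (Group 2).
3. Calculate a ratio only where both values are quantifiable, and show the number BLOQ beside it. SAP 9.1 sets BLOQ values to zero for descriptive statistics, which would make a ratio zero or undefined. Leaving these pairs out without a count would understate the decline.

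These ratios do not recover the step from 2 h to 4 h, which stays a comparison between groups; marking the groups makes that visible.

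As a minor supporting display, add sampling-group columns to the baseline table and to the blood AUC and Cmax tables, with a note that similar blood levels would not prove similar rectal exposure.

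The cost is a plotting change, one additional set of descriptive ratio tables and a few columns. No new samples, formal tests, or changes to sample size or randomisation are needed.
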